4.3.11 Safety Analysis

The analysis of the safety variables will be based on the Safety Population.

4.3.11.1 Adverse Events

The following listing and tables will be produced:

- All Pre-treatment and treatment-emergent AE [Listing 16.2.7].
- All Serious AEs (if applicable) [Listing 14.3.2.1].
- All Adverse Events Leading to Discontinuation (if applicable) [Listing 14.3.2.2].

The following information will be included in the listings: Verbatim, system organ class (SOC), preferred term (PT), AE onset date (and time) and study day, AE end date (and time) and duration (days), severity, relationship to IMP, AE outcome, TEAE indicator flag and SAE indicator flag.

An overall summary of all treatment-emergent adverse events [Table 14.3.1.1] will present the number and percentage of subjects, as well as number of events, according to the following categories:

- All treatment emergent adverse events
- Emergent adverse events Related to IMP

PAREXEL International Statistical Analysis Plan

- Mild treatment emergent adverse events
- Moderate treatment emergent adverse events
- Severe treatment emergent adverse events
- Serious treatment emergent adverse events
- Treatment emergent adverse events leading to early termination
- Deaths

Other summary tables for adverse events will include:

- Table 14.3.1.2: Number and Percentage of Subjects with Treatment Emergent Adverse Events by System Organ Class, and Preferred Term
- Table 14.3.1.3: Number and Percentage of Subjects with Treatment Emergent Adverse Events by System Organ Class, Preferred Term, and Severity
- Table 14.3.1.4: Number and Percentage of Subjects with Treatment Emergent Adverse Events “Related to IMP” by System Organ Class, Preferred Term, and Severity
- Table 14.3.1.5: Number and Percentage of Subjects with Treatment Emergent Adverse Events “Not Related to IMP” by System Organ Class, Preferred Term, and Severity

If a subject has multiple AEs with the same preferred term but occurring after each dose administration, then one AE will be counted for each treatment.

Adverse event summaries will be ordered in terms of decreasing frequency for SOC, and PT within SOC, and then alphabetically for SOC, and PT within SOC.

4.3.11.2 Clinical Safety Laboratory Tests (biochemistry, hematology, coagulation, and urinalysis)

Laboratory values (biochemistry, hematology, coagulation, and urinalysis) will be listed [Listings 16.2.8.1, 16.2.8.2, 16.2.8.3, and 16.2.8.4 respectively]. The baseline for the laboratory values will be the results obtained on Day -1; if this is missing then the screening value or, if available, a pre-dose unscheduled measurement will be used (whichever is closer to the baseline date).

PAREXEL International Statistical Analysis Plan

All values outside the clinical reference ranges will be flagged in the data listings. The abnormal values will be flagged with 'L' for values below the lower limit of the clinical reference range and 'H' for values above the upper limit of the clinical reference range and included in the listings. The Investigator will assess whether the values outside the clinical reference range are clinically significant and these will be reported as abnormal not clinically significant (NCS) or abnormal clinically significant (CS). Clinically significant laboratory values will be recorded by the Investigator as AEs.

Individual results of laboratory tests from serum chemistry, hematology, coagulation, and urinalysis outside of the laboratory normal ranges will be listed by subject, laboratory group, test and time point [Listings 14.3.4.1, 14.3.4.2, 14.3.4.3, and 14.3.4.4 respectively].

Baseline and post-dose visit data will be summarized for all serum chemistry [Tables 14.3.5.1.1 (observed) and 14.3.5.1.2 (change from baseline)], hematology [Tables 14.3.5.2.1 (observed) and 14.3.5.2.2 (change from baseline)], coagulation [Tables 14.3.5.3.1 (observed) and 14.3.5.3.2 (change from baseline)], urinalysis [Tables 14.3.5.4.1 (observed) and 14.3.5.4.2 (change from baseline)]. Observed and change from baseline for quantitative data will be summarized. Descriptive summary statistics will include n (number of observations), mean, SD, median, minimum, maximum.

Laboratory shift tables from baseline to each post-dose visit will be presented for serum chemistry [Table 14.3.5.5], hematology [Table 14.3.5.6], coagulation [Table 14.3.5.7], and urinalysis [Table 14.3.5.8].

4.3.11.3 Vital Signs

Height, weight, BMI and Body temperature will be listed [Listing 16.2.9.1.1].

Blood pressure, heart rate and respiratory rate observed and change from baseline data will be listed [Listings 16.2.9.1.2 and 16.2.9.1.3 separately]. Baseline will be taken as the pre-dose assessment on Day 1; if this is missing then the screening value or, if available, a pre-dose unscheduled measurement will be used (whichever is closer to the baseline date).

Observed values and changes from baseline will be summarized [Tables 14.3.6.1 and 14.3.6.2].

PAREXEL International
Statistical Analysis Plan

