3. OVERALL DESIGN AND PLAN OF THE STUDY

3.1. Overview

This is a phase 1, randomized, placebo-controlled, double-blind, single ascending dose study to investigate the safety, tolerability, PK/PD of the IV administration of VIS649 in healthy subjects.

The study will be conducted in four sequential dosing cohorts enrolling nine subjects per cohort, with an optional fifth cohort. Each cohort will have 4 Japanese subjects. Subjects will be randomized to VIS649 or placebo in a ratio of 7:2 (7 active, 2 placebo). No more than one Japanese subject per cohort may be randomized to receive placebo. Safety, PK and PD data from the initial cohorts will be assessed, to determine whether to initiate a fifth dosing cohort at a dose not to exceed 20 mg/kg.

The study comprises of:

- A Screening Visit up to 28 days before dosing
- An in-house stay for approximately 2-3 days, with admission to the study center on Day -1, dosing on Day 1, and discharge in the morning of Day 2
- A post-administration period of 16 weeks
- Outpatient visits, on Day 3 (+1 day), 7 (\pm 1 day), 14, 21, 28, 35, 42, 49, 56, 70, 84 and 98 (all visits \pm 3 days)
- A final Follow-up visit on Day 112 (\pm 3 days); Two additional follow-up visits may occur, at Weeks 20 and 24 post-dosing, if serum immunoglobulins have not returned to $>$ lower limits of normal by the Week 16 (Day 112) visit, or if emerging trial data suggest a value of later follow-up (i.e., for detection of ADA responses).

The total duration of the clinical study per subject will be up to approximately 20 weeks (5 months), including the Screening period with the possibility of duration extending to 28 weeks (7 months) if follow-ups visits are required.

Potential subjects will be carefully screened for eligibility prior to study enrollment. Randomization and blinding will occur according to a core randomization list administered by the site's unblinded pharmacist.

Eligible subjects will report to the Clinical Pharmacology Unit (CPU) at study check-in (Day -1) and will be required to stay in the CPU until Day 2 (24 hours post infusion). On Day 1, a single

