1. The first two subjects of each cohort will be discharged 24 hours (Day 2) after the study infusion. All other subjects are discharged on Day 2, 24 hours after study infusion. Discharge from the Phase 1 unit will not occur prior to performing the 24 h post infusion study procedures.

Visterra Inc.
VIS649-101

Final 1.0
3/Jun/2019

TP-EP.BS-WW-001-05
Effective date: 29 Jul 15
Related to: SOP-EP.BS-WW-002

PAREXEL International
Statistical Analysis Plan

2. Optional Visit at Week 20 is only to be made if immunoglobulin levels (IgG, IgM, or IgA) have not returned to normal range by Week 16; the Optional Visit at Week 24 is only to be made if immunoglobulin levels have not returned to normal range by Week 20. If immunoglobulin levels (IgG, IgM, or IgA) have not returned to normal range by Week 16 for one or more subjects, the entire cohort will complete Week 20 and Week 24.
3. Vitals signs at Screening and Day -1 will include height and weight, to permit estimated creatinine clearance calculation, as well as blood pressure (bp), heart rate (hr), respiratory rate (rr) and temperature. Subject weight will be measured after admission to the research unit (Day -1) and will be used by pharmacy staff for subject-specific dose calculation. Vital signs at other timepoints will be limited to temperature (Day -1 and Day 1 pre-dose only), bp, hr, and rr. Vital signs measurements on Day 1 will be recorded within 30 minutes prior to the start of the infusion, then every 15 minutes until the infusion is complete and post infusion at 60 minutes, 2 hours and 4 hours. On subsequent visits, vital signs will be recorded, as possible, at approximately the same time of day, if convenient. Post-dose bp should be based on the end of infusion time.
4. On Day 1 electrocardiograms will be done within 30 minutes prior to infusion and at the end of the infusion (+10 min).
5. On the day of study infusion (Day 1), blood samples for PK analysis will be collected prior to start of the infusion, at the end of infusion (60 minutes), and at 2 hours, 8 hours, and 24 hours post end of infusion. All subjects will have PK samples drawn on Days 3, 7, and Weeks 2 (Day 14), 4 (Day 28), 6 (Day 42), 8 (Day 56), 10 (Day 70), and 16 (112).

■ [REDACTED]
■ [REDACTED]
■ [REDACTED]

7. This sampling will not be done for cohort 5.
9. This sampling will be pre-vaccination in cohort 5.

PAREXEL International Statistical Analysis Plan

Cohorts are planned as follows:

Table 2 Cohorts and Dose Administration

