4.3 Statistical Analysis Methods

4.3.1 Listings and Descriptive Statistics

All original and derived parameters will be listed. Listings will be by cohort, dose, subject and, where applicable, time post dose.

All listings will include repeated and unscheduled measurements.

The following rules will apply to any repeated measurements:

- If the repeated measurement occurs prior to the first dose of study drug, then the last obtained value of any repeated measurement will be used in the descriptive statistics.
- If the repeated measurement occurs after the first dose of study drug, then the original value of any repeated measurements will be used in the descriptive statistics.

Frequency counts (number of subjects [n] and percentages) will be presented for each qualitative variable. Descriptive statistics (n, mean, standard deviation [SD], median, minimum and maximum) will be calculated and presented for each quantitative variable (unless otherwise stated).

PAREXEL International Statistical Analysis Plan

The rules with regards to the presentation of the frequency counts (number of subjects [n] and percentages) are as follows: if frequency count is 0, percentage will not be presented; if percentage is 100%, no decimal places will be given.

All descriptive statistics will be presented by treatment (dose). Subjects who receives placebo within cohort 1 - 4 will be presented as pooled placebo group, and subjects receiving placebo within cohort 5 will be used as individual placebo group as well. Data grouped from cohort 1-4, cohort 5 only and overall (all cohorts) may be analysed separately. In addition, a pooled VIS649 group (i.e. all subjects who receive VIS649 regardless of dose) will be presented for demographics, disposition, and adverse event. The baseline for all measurements (where applicable) will be the last pre-dose measurement unless specified.

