4.3.11.4 Twelve-Lead Electrocardiogram

The individual data and investigators overall interpretation of the 12-lead ECG results and change from baseline will be listed [Listings 16.2.9.2.1 and 16.2.9.2.2 separately]. Baseline will be taken as the pre-dose assessment on Day 1; if this is missing then the screening value or, if available, a pre-dose unscheduled measurement will be used (whichever is closer to the baseline date).

Observed values and changes from baseline will be summarized [Table 14.3.7.1 and 14.3.7.2].

The incidence of abnormalities, based on the clinical interpretations from the investigator, will be counted by treatment and visit [Table 14.3.7.3].

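### The fallback baseline for vital signs and ECG passes over the scheduled Day -1 reading, so a Screening value up to 28 days old can replace one taken the day before dosing

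*SAP*

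**What the plan says.** SAP 4.3.11.3 defines the vital-sign baseline: "Baseline will be taken as the pre-dose assessment on Day 1". If that value is absent, the section continues: "if this is missing then the screening value or, if available, a pre-dose unscheduled measurement will be used (whichever is closer to the baseline date"). SAP 4.3.11.4 repeats the rule for ECG: "Baseline will be taken as the pre-dose assessment on Day 1; if this is missing then the screening value", with the same unscheduled alternative and the same closeness condition.

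SAP Table 1 (section 3.1) marks vital signs and ECG on three occasions up to dosing: Screening, the Baseline column (Day -1), and Day 1. Footnote 3 confirms what is taken on Day -1: "Vitals signs at Screening and Day -1 will include height and weight, to permit estimated creatinine clearance calculation, as well as blood pressure (bp"), with heart rate and respiratory rate following in the same sentence. Footnote 4 covers the Day 1 recording: "On Day 1 electrocardiograms will be done within 30 minutes prior to infusion".

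SAP 4.3.1 sets a default: "The baseline for all measurements (where applicable) will be the last pre-dose measurement unless specified".

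**The concern.** The fallback names two substitutes, Screening and unscheduled. The Day -1 reading is scheduled and has its own visit, so it is neither. The rule therefore leaves out the closest scheduled alternative, at the visit the study itself calls Baseline.

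Change from baseline in blood pressure, heart rate and ECG intervals, including QTcF, is summarised by dose in Tables 14.3.6.2 and 14.3.7.2 and listed in Listings 16.2.9.1.3 and 16.2.9.2.2. For ECG, only one post-dose recording is scheduled, at the end of infusion. Each subject's ECG change is thus one post-dose value minus one baseline, and no later scheduled ECG can offset a poor reference.

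**Working it through.** The plan states no figure to reproduce. The check sets the rule against the visit schedule and counts days.

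**Which pre-dose values exist, and which the rule can reach when the Day 1 value is missing**

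| Pre-dose value | In SAP Table 1 | Days before Day 1 (no Day 0) | Reached by 4.3.11.3 / 4.3.11.4 | Reached by 4.3.1 default |
|---|---|---|---|---|
| Screening | Ambulatory visit, Day -28 to Day -1 | up to 28 | Yes | Only if nothing later exists |
| Scheduled Day -1 | In-house day, Baseline column | 1 | No | Yes, unless a later unscheduled value exists |
| Unscheduled pre-dose | Not scheduled | Any | Yes, if closer than Screening | Yes, if last |

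**Can Screening be read to include Day -1?** The Screening window nominally ends on Day -1, but Table 1 gives Day -1 its own column and shows Screening as ambulatory and Day -1 as in-house. SAP 4.3.6.7 also treats screening and check-in as separate occasions. The reading does not hold.

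**Does the default in 4.3.1 repair it?** No. It applies only where nothing else is specified, and both sections specify a fallback.

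**Does the closeness condition repair it?** No. It chooses between the two named candidates and does not add a third. Whether the baseline date means Day 1 or Day -1, the Day -1 reading is 1 or 0 days away, so the rule excludes the scheduled value that best meets its own aim. Taken literally, an unscheduled reading on Day -1 would qualify while the scheduled reading from the same day would not.

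**Where the wording does work.** SAP 4.3.11.2 uses the same fallback for laboratory tests. There the primary baseline is already Day -1, so Screening is the next scheduled value back. For vital signs and ECG the primary baseline is Day 1, and the same sentence skips a visit.

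**Age of the substitute baseline, with no unscheduled value**

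- As written: up to 28 days. SAP Table 1 and the Protocol text agree (Protocol 3.1: "A Screening Visit up to 28 days before dosing"). The header of Protocol Table 9 opens the window at Day -30, which would make it up to 30 days.
- Under the 4.3.1 default: 1 day.

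**Weight of one affected subject in a group mean change** (1/n, group sizes from SAP Table 2)

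- Active, each of Cohorts 1 to 4: 1/7 = 14.3%
- Active, Cohort 5: 1/10 = 10%
- Pooled placebo, Cohorts 1 to 4: n = 4 × 2 = 8, so 1/8 = 12.5%
- Placebo, Cohort 5: 1/5 = 20%

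If a subject's Screening value differs from the Day -1 value by d, the group's mean change moves by d/n. The documents give no basis for a value of d.

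**Number of subjects affected.** The documents give no rate of missing Day 1 readings. The working assumption is 0 to 2 of the 51 planned subjects (4 × 9 + 15 = 51).

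**The case against.** The strongest reply is that the intent is plain and the effect close to nil. The closeness condition and the 4.3.1 default both point to the nearest pre-dose value, and the match with the laboratory section suggests copied wording, not a decision to discard Day -1. The Day 1 readings are taken in-house within 30 minutes before infusion, in subjects admitted the day before, so they will seldom be missing. The outputs are descriptive. Observed values are tabulated separately and all values are listed, so the Day -1 reading stays visible. The vital-sign and ECG stopping criteria in Protocol 3.4 use absolute thresholds, and the primary endpoint counts adverse events. Neither uses this baseline. Finally, 1/7 is a weight in a mean and not an estimate of bias, and 28 days is the outer limit of the window.

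All of this bears on size, and as to size it stands. That an ambulatory Screening value is a poorer reference than the in-house value of the day before is also a judgement; the documents do not show it. None of this changes the text. A programmer who follows 4.3.11.3 literally will derive a different baseline from one who follows 4.3.1, and a SAP should prevent that. If the sentence is a drafting slip, that is a reason to correct it.

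**Conclusion.** The concern holds for both vital signs and ECG. As written, the fallback skips the scheduled Day -1 reading and can substitute a Screening value up to 28 days old for one that is 1 day old. The general last-pre-dose rule does not cure this, because the specific sections override it.

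The point is minor. It takes effect only if a Day 1 pre-dose value is missing (0 to 2 of 51 is an assumption, and zero would mean no effect), and a nearby unscheduled value would shorten the gap. Its reach is limited to the descriptive change-from-baseline tables and listings for vital signs and ECG. No stopping criterion for these variables and no primary-endpoint count depends on it.

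**What to change.** In SAP 4.3.11.3 and 4.3.11.4, replace the fallback with a rule of this kind: *when the Day 1 pre-dose value is missing, baseline is the latest available measurement before the start of infusion, whether scheduled (Day -1 included) or unscheduled; Screening serves only when nothing later exists.* This agrees with 4.3.1 and leaves the primary baseline definition unchanged. The laboratory section can stay as it is.

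The cost is one sentence in each of two sections, with no new data. It should be made before database lock, because the SAP sends later departures to an addendum.

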4.3.11.4 Twelve-Lead Electrocardiogram

The individual data and investigators overall interpretation of the 12-lead ECG results and change from baseline will be listed [Listings 16.2.9.2.1 and 16.2.9.2.2 separately]. Baseline will be taken as the pre-dose assessment on Day 1; if this is missing then the screening value or, if available, a pre-dose unscheduled measurement will be used (whichever is closer to the baseline date).

Observed values and changes from baseline will be summarized [Table 14.3.7.1 and 14.3.7.2].

The incidence of abnormalities, based on the clinical interpretations from the investigator, will be counted by treatment and visit [Table 14.3.7.3].

4.3.11.5 Physical Examination

The abnormal results of the physical examination will be listed [Listing 16.2.9.3].

4.3.11.6 Response to Tetanus/Diphtheria Vaccination

Tetanus and diphtheria immunity are assessed by measurement of anti-tetanus and anti-diphtheria toxoid IgG serum levels, respectively, by neutralization assay or by.

For cohort 5, IgG data of Tetanus/diphtheria serology assessment will be listed [Listing 16.2.8.5]. Summary of observed and change from baseline for IgG will be tabulated [Tables 14.3.5.9]. Serum IgG level for tetanus and diphtheria following a dose of TENIVAC vaccine will be summarized separately by treatment, timepoints [Tables 14.3.5.10, 14.3.5.11]. Levels of serum IgG for tetanus: >0.1IU/mL and >1.0 IU/mL and levels of serum IgG for diphtheria: >0.01IU/mL, >0.1IU/mL and >1.0 IU/mL will be used for summary.

PAREXEL International
Statistical Analysis Plan

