4.1.4.2 Clinical Laboratory Tests

The following safety laboratory parameters will be measured (Table 2) in the study.

Table 4 Clinical Laboratory Assessments

Hematology	
White blood cell (WBC) count	Neutrophils (percentage and absolute count)
Red blood cell (RBC) count	Lymphocytes (percentage and absolute count)
Hemoglobin (Hb)	Monocytes (percentage and absolute count)
Hematocrit (HCT)	Eosinophils (percentage and absolute count)
Mean corpuscular volume (MCV)	Basophils (percentage and absolute count)
Mean corpuscular hemoglobin (MCH)	Platelet count
Mean corpuscular hemoglobin concentration (MCHC)	RBC distribution width
Coagulation	
Prothrombin time (PT)	International Normalized Ratio (INR)
Activated partial thromboplastin time (aPTT)	
Clinical Chemistry	
Alanine aminotransferase (ALT)	Glucose
Albumin	Lactate dehydrogenase (LDH)
Alkaline phosphatase (ALP)	Phosphorus
Aspartate aminotransferase (AST)	Potassium
Blood urea nitrogen (BUN)	Sodium
Calcium	Total bilirubin
Chloride	Total protein
Cholesterol	Triglycerides
Creatinine	Uric acid

PAREXEL International
Statistical Analysis Plan

Gamma glutamyl transferase (GGT)	FSH (Screening Visit only; all female subjects)
Urinalysis	
Bilirubin	Blood
Glucose	pH and specific gravity
Ketones	Protein
Leukocytes	Urobilinogen
Nitrite	Microscopic (only for abnormal urine stick test findings)
Viral Serology	
Human immunodeficiency virus (HIV) (Types 1 and 2) antibodies	Hepatitis C virus antibody (anti-HCV)
Hepatitis B surface antigen (HBsAg)	
Serology	
Tetanus/diphtheria serology	
Urine Drug Screening and Cotinine Test	
Amphetamines	Cocaine
Barbiturates	Opiates
Benzodiazepines	Phencyclidine
Cannabinoids	Cotinine
Urinary creatinine (to exclude dilution effect)	Ethanol
Pregnancy Testing	
Serum/urine human beta chorionic gonadotrophin (women of childbearing potential only)	

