PAREXEL International
Statistical Analysis Plan

Listing 14.3.4.1 Clinical Laboratory Chemistry Measurements Outside Normal Range (Safety Population)

Listing 14.3.4.2 Clinical Laboratory Hematology Measurements Outside Normal Range (Safety Population)

Listing 14.3.4.3 Clinical Laboratory Coagulation Measurements Outside Normal Range (Safety Population)

Listing 14.3.4.4 Clinical Laboratory Urinalysis Measurements Outside Normal Range (Safety Population)

Table 14.3.5.1.1 Clinical Laboratory Chemistry - Summary of Observed Values (Safety Population)

Table 14.3.5.1.2 Clinical Laboratory Chemistry - Summary of Change from Baseline (Safety Population)

Table 14.3.5.2.1 Clinical Laboratory Hematology - Summary of Observed Values (Safety Population)

Table 14.3.5.2.2 Clinical Laboratory Hematology - Summary of Change from Baseline (Safety Population)

Table 14.3.5.3.1 Clinical Laboratory Coagulation - Summary of Observed Values (Safety Population)

Table 14.3.5.3.2 Clinical Laboratory Coagulation - Summary of Change from Baseline (Safety Population)

Table 14.3.5.4.1 Clinical Laboratory Urinalysis - Summary of Observed Values (Safety Population)

Table 14.3.5.4.2 Clinical Laboratory Urinalysis - Summary of Change from Baseline (Safety Population)

Table 14.3.5.5 Shift from Baseline to Any Post-Dose Assessment in Laboratory Results:

PAREXEL International
Statistical Analysis Plan

Hematology (Safety Population)

Table 14.3.5.6 Shift from Baseline to Any Post-Dose Assessment in Laboratory Results: Chemistry (Safety Population)

Table 14.3.5.7 Shift from Baseline to Any Post-Dose Assessment in Laboratory Results: Coagulation (Safety Population)

Table 14.3.5.8 Shift from Baseline to Any Post-Dose Assessment in Laboratory Results: Urinalysis (Safety Population)

Table 14.3.5.9 Tetanus/Diphtheria Serology Summary of Observed and Change from Baseline Values: IgG (Safety Population Cohort 5 only)

Table 14.3.5.10 Summary of Serum Tetanus IgG (Safety Population Cohort 5 only)

Table 14.3.5.11 Summary of Serum Diphtheria IgG (Safety Population Cohort 5 only)

Vital Sign

Table 14.3.6.1 Vital Signs – Summary of Observed Values (Safety Population)

Table 14.3.6.2 Vital Signs – Summary of Change from Baseline (Safety Population)

ECG

Table 14.3.7.1 12-Lead ECG - Summary of Observed Values (Safety Population)

Table 14.3.7.2 12-Lead ECG - Summary of Change from Baseline (Safety Population)

Table 14.3.7.3 12-Lead ECG – Clinical Assessment (Safety Population)

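### Cohort 5 tetanus/diphtheria IgG should also be summarised with geometric means and a VIS649/placebo geometric mean ratio, and the Day 28 sample should be named as the reference for change

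*SAP*

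**What the plan says.** Cohort 5 randomises 10 subjects to VIS649 6.0 mg/kg and 5 to placebo, and all of them receive a tetanus/diphtheria vaccine (SAP 3.1 and Table 2). Section 4.3.11.6 states for the serology: "Summary of observed and change from baseline for IgG will be tabulated" (Table 14.3.5.9). Tables 14.3.5.10 and 14.3.5.11 then summarise tetanus IgG against 0.1 and 1.0 IU/mL and diphtheria IgG against 0.01, 0.1 and 1.0 IU/mL, by treatment and time point. Individual values go into Listing 16.2.8.5.

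Section 4.3.11.6 does not list statistics, so 4.3.1 governs: "Descriptive statistics (n, mean, standard deviation [SD], median, minimum and maximum) will be calculated and presented for each quantitative variable". Elsewhere the SAP plans geometric means for PK concentrations (4.3.7) and log10 values for ADA titers (4.3.10).

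Section 4.3.11.6 does not say which sample is the baseline either. The general rule in 4.3.1 is "The baseline for all measurements (where applicable) will be the last pre-dose measurement unless specified". The laboratory rule in 4.3.11.2 begins "The baseline for the laboratory values will be the results obtained on Day -1; if this is missing then the screening value", and SAP Table 4 includes "Tetanus/diphtheria serology". A footnote to SAP Table 1 reads "This sampling will be pre-vaccination in cohort 5".

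**The concern.** Tables 14.3.5.9 to 14.3.5.11 are the only vaccine-response summary tables visible in the SAP, and they set 10 subjects beside 5. If the levels are skewed, the mean of a five-subject arm depends heavily on its highest value, and the SD describes the spread poorly. The median avoids that, but at these sample sizes it uses the data less efficiently, and no interval is planned for it. The cut-off shares are coarse: if every subject passes, the exact 95% lower limit is still only 69% for 10 of 10 and 48% for 5 of 5. The tables would therefore offer no efficient estimate of how the two arms compare after vaccination.

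The unnamed baseline is a smaller matter. Taken as referring to study drug, both rules look for a sample that the visible schedule does not contain.

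**Working it through.** The plan states no figure to reproduce: the sample size has no formal basis (SAP 3.3), and neither a serology contrast nor a serology test is planned.

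**Inputs.** From the documents: 10 v 5 subjects, the default statistics and the cut-offs. Assumed, because the documents give no variability: log-normal IgG levels with a log10 SD of 0.4 to 0.6 in both arms.

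**Geometric mean ratio, no drug effect.** The standard error of the log10 ratio is SD × √(1/10 + 1/5) = SD × 0.5477. The 90% range is 10^(±1.645 × SE).
- SD 0.4: SE = 0.219 and 1.645 × 0.219 = 0.360, which gives 0.44 to 2.29.
- SD 0.6: SE = 0.329 and 1.645 × 0.329 = 0.541, which gives 0.29 to 3.47.

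**All three summaries of observed post-vaccination levels.** The arithmetic mean and median rows are simulated; repeat runs move the last digit (the median's upper limit at SD 0.6 falls between 4.4 and 4.5).

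| Ratio of | SD 0.4 | Upper/lower | SD 0.6 | Upper/lower |
|---|---|---|---|---|
| geometric means | 0.44-2.29 | 5.2 | 0.29-3.47 | 12 |
| arithmetic means | 0.40-2.71 | 6.8 | about 0.24-5.3 | 22 |
| medians | about 0.37-2.7 | 7.3 | about 0.23-4.4 | 19 |

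**Weight of one subject.** In simulated arms of 5, the highest level makes up a median 42% (SD 0.4) to 52% (SD 0.6) of the arm's arithmetic total.

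**Precision that remains.** The 95% CI of the geometric mean ratio is the estimate multiplied or divided by 10^(t × SE), with t = 2.160 on 13 df. This factor is 10^(2.160 × 0.219) = 2.97 at SD 0.4 and 10^(2.160 × 0.329) = 5.13 at SD 0.6. With the SD estimated from the 15 subjects, the median factor is 2.89 and 4.91.

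**Which sample can be the reference.** In SAP Table 1 as extracted, the first serology mark stands in the same column as the vaccine row and the Week 4 pre-vaccination marks. None stands at Screening, Day -1 or Day 1. That makes 0 scheduled serology samples before study drug and 1 before vaccination, at Day 28.

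**What an on-treatment reference does.** Day 28 is four weeks after the infusion. Suppose a tenfold rise in placebo (1 to 10), a VIS649 Day 28 level of 0.60 of placebo and a true post-vaccination ratio of 0.50. The 0.60 is assumed: it borrows the roughly 40% total-IgG nadir in Protocol 1.3.
- Arithmetic change, as planned: (0.5 × 10 − 0.6)/(10 − 1) = 0.49.
- Fold-rise, not planned: 0.50/0.60 = 0.83.

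With a true ratio of 1.00, the two give (10 − 0.6)/(10 − 1) = 1.04 and 1.00/0.60 = 1.67.

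**The case against.** The strongest case against is that this is a descriptive safety summary in a phase 1 study. The default already includes the median, minimum and maximum, every value is listed, and under log-normality the population median equals the geometric mean. Tenfold cut-offs do not prove log-normal data. All of that is fair. It makes the proposal an improvement in method and not the repair of an error. What remains is that the sample geometric mean is tighter than the sample median at 10 v 5, and that no interval is planned.

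Four stronger readings are tempting, and the documents do not support them.

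- A reader might infer that the change columns cannot be filled. But 4.3.1 applies its rule where applicable and unless otherwise specified, SAP 4.1.3 and 4.3.11.6 both describe the vaccine as a dose, and only one pre-vaccination sample exists. Any analyst would use Day 28. The laboratory rule is a weak rival too, because the heading of 4.3.11.2 covers biochemistry, hematology, coagulation and urinalysis only.
- A reader might infer that the Day 28 reference biases the planned table. Under the assumption above, the planned change gives 0.49 for a true 0.50; it is fold-rise that misleads. The 0.60 is itself a stretch, since it carries a predicted total-IgG nadir over to existing specific antibody after a single dose. Protocol 1.3 also says that responses to a novel antigen were not suppressed in the preclinical studies.
- A reader might infer a larger precision gain by setting arithmetic mean change against post-vaccination geometric means (upper limits of 6.73 v 3.47 at SD 0.6 and a pre/post correlation of 0.4). Those are different quantities, and observed values are planned as well.
- A reader might expect more power. For a halved level, simulated power is 26% (arithmetic change) v 25% (geometric mean) at SD 0.4 and 13% v 14% at SD 0.6, both with correlation 0.4. At SD 0.4 and correlation 0.8 it is 30% v 25%, which favours arithmetic change.

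Some of the text is also out of sight. Several Table 1 footnotes are redacted or misnumbered, a sentence in 4.3.11.6 breaks off, and the SAP follows CSP Amendment 2, whereas the protocol supplied has no vaccine cohort.

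**Conclusion.** The point holds as a modest improvement. On the visible text, cohort 5 serology receives only default statistics and cut-off shares, while the same SAP treats PK concentrations and ADA titers on a multiplicative scale. Under assumed log-normal levels, geometric means narrow the no-effect 90% range of the arm ratio from an upper/lower quotient of about 7 to about 5 at log10 SD 0.4, and from about 19-22 to 12 at SD 0.6. The comparison stays imprecise either way, with a 95% CI factor of roughly 3 to 5. The size of the gain depends entirely on the assumed distribution and SD.

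Naming Day 28 is a wording fix to go into the same edit. The evidence does not show that the planned change table would be unusable or biased.

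**What to change.** In SAP 4.3.11.6 and Table 14.3.5.9:

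1. Add geometric mean concentrations with 95% CIs by treatment at Day 28 and at each later serology visit.
2. Add the unadjusted post-vaccination VIS649/placebo geometric mean ratio with its 95% CI, as a descriptive contrast.
3. Name the Day 28 pre-vaccination sample as the reference for change.
4. If fold-rise from Day 28 is shown, label it exploratory and note that Day 28 is four weeks after study drug, so that it does not measure the total drug effect.
5. State how values below the assay limit enter the geometric mean. SAP 4.3.8 already sets such PD values to the LLOQ, and one line could extend that rule to the serology.

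Keep the planned statistics, the cut-off tables and the listing. The cost is a few sentences and table rows, with no extra subject, sample or assay. Before editing, check the legible Table 1 footnotes and CSP Amendment 2, which may already name the reference.
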